5.1 General study design

Sixty subjects will be enrolled on this single-arm Phase II study investigating the efficacy and safety of omitting postoperative RT to the primary tumor site in patients with locally-advanced (stage III or IVa) HPV+ oropharynx cancer who undergo TORS resection and neck dissection. Patients will be required to have a negative surgical margin (defined as 2mm or greater) after

resection of the primary site for a pathologic T1 or T2 cancer, with no evidence of perineural invasion.

Patients will be treated to the regional nodes, per current clinical standards, to a total dose of 60-66 Gy over 30-33 fractions, as determined by current clinical guidelines for postoperative radiation therapy (10-12). Both IMRT and PBRT will be allowed. Platinum-based chemotherapy will be delivered concurrently with RT, as clinically indicated for ECE (10-12).

Clinical, toxicity and QOL evaluations will be obtained at baseline (prior to RT), and completion of RT, and then at approximately 3, 6, 12, 18 and 24 months after completion of RT, during routine clinical follow-up appointments. Routine clinical follow-up will continue after this time point, at the discretion of the treating physicians.

Local recurrence will be defined as biopsy-proven recurrent squamous cell carcinoma at the original, primary tumor site.

Study Visit Schedule & Procedures

	*Baseline	End RT	**3mo. post RT	**6mo. post RT	**12mo. post RT	**18mo. post RT	**24mo. post RT
ICF	x						
Eligibility	x						
PE	x	x	x	x	x	x	x
QOL form	x	x	x	x	x	x	x
Tox. Assessment		x	x	x	x	x	x

*prior to RT ** approximately

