5.3 Radiation Therapy

Simulation for treatment is required. CT-based treatment planning is required. Treatment with either IMRT or PBRT is allowed. All fields will be treated every session. Interruptions in therapy should be discussed with the principal investigator but will be instituted at the discretion of the attending radiation oncologist.

Dose calculation should be performed using inhomogeneity corrections to account for differences in tissue density across the head and neck region. The total dose to regional lymph nodes will be 60-66 Gy to high-risk regions over 30-33 fractions, and 54 Gy to low-risk regions over 30 fractions. The primary tumor bed will be excluded from receiving high-dose radiation. Treatment will be continuous, 5 days per week for 6-7 consecutive weeks.

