We anticipate enrolling roughly 60 subjects over a period of 12 months, following each subject for up to 24 months. Because no patient will have reached the 24-month follow-up limit by the time enrollment ends, interim safety analyses will rely on model-based estimates of the rate of local recurrence using available time-to-event data. We will conduct an interim analysis for safety at the one-year mark (one year after completion of enrollment), when the median follow-up is 1.5 years (minimum = 1 and maximum = 2 years). We will fit an exponential model to the data on time to local recurrence. We will estimate the overall exponential hazard rate, comparing it to the null hazard rate of 0.00214 (predicting 5% recurrence at 24 months) in a two-tailed test with type I error rate 2.5% (to adjust for multiplicity). Should the estimated hazard rate significantly exceed the null rate, we will consider halting the trial for concern about safety. We will conduct the test when follow-up is complete (two years after completion of enrollment), again at the 2.5% type I error rate.

7 Safety and Adverse Events

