7.2 Stopping Rules

As noted in section 6.0, based on results of an interim analysis for safety at the one-year mark, we will consider halting the trial for safety if the estimated hazard rate significantly exceeds the null rate.

8 Data Handling and Record Keeping

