8.3 Flow of Subject Data

Study entry: Each patient will be screened and evaluated for this study based upon the inclusion and exclusion criteria. If a patient is found to be potentially eligible for the study the patient will be approached for participation in this study, and if they are interested, they will be asked to sign an informed consent form. An eligibility checklist will be completed and signed by the PI verifying eligibility. The patient will be assigned a study number. A list of the subjects with the assigned study numbers will be kept in a locked cabinet with the study charts as well as on a confidential computer file in the Department of Radiation Oncology, University of Pennsylvania. The study coordinator and principal investigator will maintain the locked cabinet. All study forms: eligibility forms, on study forms, case report forms (CRF), toxicity forms, and data entry forms will be coded with the subject's study number to protect subject confidentiality.

Treatment: After study enrollment, the subject will undergo treatment planning for radiotherapy as per standard clinical care. The principal or a co-investigator will fill out a radiotherapy prescription form as per routine clinical care. A hard copy of the radiotherapy prescription form, radiotherapy treatment plan, and dose-volume histograms will be placed in the subject's study chart.

Follow-up: The clinical status of the subjects will be recorded on a flow sheet and on the CRF and maintained in the subject's study chart. QOL forms and toxicity grading will be performed at baseline, at end of treatment, at approximately 3, 6, and 12, 18, and 24 months after treatment. At approximately 24 months after completion of RT, the subject will be considered "off-study", but will continue routine clinical follow-up as per routine clinical guidelines.

9 Data and Safety Monitoring Plan

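### The only numerical local-recurrence stopping test comes a year after enrolment ends, so it cannot limit exposure, and the Medical Monitor has no agreed recurrence count to act on during accrual

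*Combined protocol and SAP*

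**What the plan says.** Section 6 (Interim analysis) plans one interim safety test: "We will conduct an interim analysis for safety at the one-year mark (one year after completion of enrollment". An exponential model is fitted to time to local recurrence and its hazard is compared with 0.00214 per month (5% at 24 months), "in a two-tailed test with type I error rate 2.5% (to adjust for multiplicity". The test is repeated two years after enrolment ends, when follow-up is complete. On method, the section says: "Because no patient will have reached the 24-month follow-up limit by the time enrollment ends, interim safety analyses will rely on model-based estimates".

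Section 7.2 refers back to that analysis: "we will consider halting the trial for safety if the estimated hazard rate significantly exceeds the null rate". It sets no other criterion.

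Section 5.3 gives the length of RT: "Treatment will be continuous, 5 days per week for 6-7 consecutive weeks". Section 5.1 schedules assessments at baseline, at the end of RT, "and then at approximately 3, 6, 12, 18 and 24 months after completion of RT, during routine clinical follow-up appointments", and defines the event: "Local recurrence will be defined as biopsy-proven recurrent squamous cell carcinoma at the original, primary tumor site".

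Section 9.3 provides a Medical Monitor who meets the team biannually or more often, reviews safety and activity data, may recommend suspension or termination, and is told whether the data met any of the protocol's stopping criteria. Section 7.1 requires an alert within five business days for events of grade 3 or higher.

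**The concern.** A safety rule that can lead to halting a trial normally protects patients not yet treated. This one is tied to the end of enrolment, so whether accrual is fast or slow, nobody is left to protect when it is first applied. It can still inform conclusions and the follow-up of treated patients.

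During accrual, the Monitor is to be told whether stopping criteria were met, but no local-recurrence criterion applies then. The grade 3 alert is not a dependable substitute: section 7.1 ends adverse event reporting 30 days after the last study treatment, before the 3-month visit, and nothing says that a biopsy-proven recurrence goes through that route.

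The protocol describes the approach as new in this population. Its cited support is a series of 30 surgery-only patients with 97% local control. If that means 1 failure in 30 (an assumption), the exact 95% interval for failure is 0.08% to 17.2%, and the upper limit is close to the plan's own 17.5% alternative. The comparison is rough: 83% of that series were T1-2, whereas this trial also excludes T3-4 disease, margins under 2 mm, PNI and LVI.

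**Working it through.** **1. The plan's own figures.** Null hazard = -ln(0.95)/24 = 0.002137 per month, which rounds to the stated 0.00214. Uniform accrual over 12 months, read at month 24, gives follow-up of 1 to 2 years with median 1.5, as stated.

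**2. Who is still untreated at the first test.** Enrolment ends at month 12 and the test falls at month 24. A patient enrolled at month 12 who starts RT promptly finishes by 12 + 7/4.345 = month 13.6. Section 8.3 places planning after entry ("After study enrollment, the subject will undergo treatment planning for radiotherapy as per standard clinical care") but gives no interval. The delay to RT would have to exceed 24 - 13.6, about 10 months, for anyone to be still on RT. Exposures the formal rule can prevent: 0 of 60.

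**3. Power of that test.** Person-time is about 60 × 18 = 1,080 months, so 1,080 × 0.002137 = 2.31 recurrences are expected under the null. At 17.5%, power is about 71% with an exact Poisson test (7 events needed) or 83% with a log-Wald test. The plan names only the exponential model, so both test forms are assumptions.

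**4. What a check during accrual would see.** At 5 patients per month, person-time from enrolment at month m is 5m²/2.
- Month 6: 90 person-months, 0.19 expected under the null; P(≥2) = 0.0163, P(≥3) = 0.0010.
- Month 9: 202.5 person-months, 0.43 expected; P(≥2) = 0.0706, P(≥3) = 0.0098.

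At the plan's upper tail of 2.5%/2 = 1.25%, the trigger is 3 at each look. It is not general. Counting from the end of RT (assumed 2 months after enrolment), month 6 has 5 × 4²/2 = 40 person-months and P(≥2) = 0.0035, so the triggers become 2 then 3. The log-Wald form counted from enrolment also gives 2 then 3.

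**5. Chance of a flag by month 9, and mean patients not enrolled (trigger 3 at each look).** Simulated with constant hazard; the 30% and 40% rates are assumed. A flag at month 6 leaves 30 patients unenrolled, and one at month 9 leaves 15.

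| True two-year rate | (a) Found at scheduled visits, risk from enrolment | (b) Found at visits, risk only after RT | (c) Found at once, risk from enrolment |
|---|---|---|---|
| 5% (false pause) | 0.4% | 0.1% | 0.9% |
| 17.5% | 11%; 1.7 | 2%; 0.3 | 21%; 3.5 |
| 30% | 35%; 5.7 | 9%; 1.4 | 55%; 10.2 |
| 40% | 57%; 9.8 | 20%; 2.9 | 78%; 15.6 |

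Scenario (c) is an upper bound. In (a) and (b) the 3-month visit falls 5 months after enrolment, so only 5 × 1 = 5 patients have passed it at month 6 and 5 × 4 = 20 at month 9. Month 6 alone flags about 0.9% in (a) and 0.01% in (b) at 17.5%.

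**6. A running count of 3 throughout accrual.** Flags at 17.5%: about 34% in (a), 14% in (b), 54% in (c). False pauses at 5%: about 1.9%, 0.6% and 4%. The last agrees with the Poisson figure at month 12: 360 person-months, 0.77 expected, P(≥3) = 0.043. A fixed count of 3 is thus looser than the 1.25% tail late in accrual, where the exact trigger is 4 (P(≥4) = 0.0080).

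**7. Overall chance of any flag at a true 5%.** Exact: about 1.3% for the plan's two looks, 2.0% with months 6 and 9 added. Log-Wald: 3.8% and 5.4%. For the running count with exact later tests, the sum 4% + 1.3% = 5.3% is a ceiling.

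**The case against.** The strongest reply is that the deferral is sensible. With 0.19 to 0.43 events expected under the null at months 6 and 9, an early test can say little, whereas the planned one has about 71-83% power. At the plan's own alternative, two added looks flag only 2-11% under visit-based detection, and the larger gains need rates of 30-40% that nothing in the protocol supports. That stands, and it limits what the addition can claim.

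The timing also matters. Twice-yearly meetings guarantee only month 6 within a 12-month accrual, and that look adds almost nothing; month 9 would be an extra review. Added looks also raise overall error unless it is re-allocated. Both points stand and shape the fix.

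A reader might infer that local recurrence goes unsupervised during accrual. The documents do not support that: section 9.2 places the study in the high-risk audit category, section 9.1 makes the investigators responsible for continuous monitoring, and the Monitor sees activity data and can recommend suspension without a written count. For the same reason, the patients-not-enrolled figures are not the net gain. They compare the added check with the formal rule alone, and three biopsy-proven recurrences among so few evaluable patients might well prompt action anyway.

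A reader might also take the sentence about no patient reaching 24 months as a mistaken defence of the timing. It only explains why the estimates are model-based. It neither justifies waiting nor rules out an earlier look, since the same model accepts censored data.

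**Conclusion.** The point holds as a design gap worth considering. The single pre-specified numerical rule is first applied when it can prevent 0 of 60 exposures, and no recurrence count guides the Medical Monitor while patients can still be spared. This rests on the text and the 6-7 week RT course, and fails only if RT starts some 10 months after enrolment. Confidence in the gap is high.

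The value of closing it is modest and less certain. Under uniform 12-month accrual and constant hazard, an accrual-period count would detect a true 17.5% rate in a minority of trials under visit-based detection (2-11% with two looks, 14-34% with a running count). Its main use is against much higher rates, and its benefit comes on top of existing oversight by an amount that cannot be quantified from the documents. It would be wrong to conclude that the trial is unmonitored, that the later tests are without use, or that an early look would reliably have caught 17.5%.

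**What to change.** In sections 6 and 7.2, add a criterion that pauses accrual for Medical Monitor and DSMC review once a pre-stated number of biopsy-proven local recurrences is reached.

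- Derive the number from the null hazard of 0.00214 per month and actual person-time, and state the time origin (enrolment or end of RT) and the test form.
- Apply it as each recurrence is confirmed, or at looks explicitly added at months 6 and 9. Do not rely on the biannual meetings alone. If accrual runs past 12 months, continue until it closes.
- If a fixed count of 3 is used throughout, say that it is looser than the 1.25% tail towards the end of accrual.
- Report the operating characteristics, including the low sensitivity at 17.5%, and the overall error with the added looks. State that the benefit is additional to Monitor oversight and smaller than the patients-not-enrolled figures suggest.
- Keep the tests at one and two years after enrolment ends.

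The cost is protocol wording and short analyses of data already collected. The chance of an unnecessary pause at a true 5% is 1% or less for two exact looks, about 2% with the log-Wald triggers, and about 0.6-1.9% (at most 4%) for the running count. The overall flag rate rises as shown in step 7 of the working. The pause leads to review, not to an automatic stop, and no treatment rule changes.

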HRQoL evaluations will be obtained at baseline and completion of RT, and then approximately at 3, 6, 12, 18 and 24 months after completion of RT. We will estimate mixed linear models predicting HRQoL from treatment stratum, demographic and baseline clinical criteria. It is necessary to adjust for these factors to reduce potential confounding bias, as the treatments will not be randomized.

Sample size justification

With 30 patients per stratum, we will have 78% power to detect a difference in failure of 2-year local control, assuming a null rate of 5% and an alternative rate of 17.5%, using a one-tailed exact binomial test with type I error rate 10%.

Also with 30 patients per stratum, we will have 90% power to detect a difference in stratum means of HRQoL outcomes, provided that the effect size (absolute difference in means divided by common standard deviation) is larger than 0.86. This calculation assumes a two-tailed Student *t* test with type I error rate 5%.

Given that the decision to treat with IMRT vs PBRT is not randomized, but rather based on current insurance approval/denial patterns, we expect there to be an approximate 1:1 ratio of IMRT:PBRT; however, this study will not obligate 1:1 IMRT:PBRT. The comparison of IMRT to PBRT is a secondary objective of the study, and inability to populate the strata in a 1:1 ratio will not impede evaluation of the data for the primary objective. If recruitment goals are not met for each stratum, adjustments will be made to the data analysis as it pertains to the secondary objective of comparing IMRT to PBRT.

Interim analysis

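### The local-recurrence safety test acts only on an excess but is two-tailed at 2.5% per look with no test statistic named; an upper one-tailed 2.5% test never detects less harm and usually detects more

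*Combined protocol and SAP*

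**What the plan says.** Section 6, Interim analysis, sets the expected course: "We anticipate enrolling roughly 60 subjects over a period of 12 months, following each subject for up to 24 months". The method is: "We will fit an exponential model to the data on time to local recurrence". The overall hazard is tested at the interim, one year after enrollment ends, "comparing it to the null hazard rate of 0.00214 (predicting 5% recurrence at 24 months"), and this is done "in a two-tailed test with type I error rate 2.5% (to adjust for multiplicity"). A second look follows: "We will conduct the test when follow-up is complete (two years after completion of enrollment), again at the 2.5% type I error rate".

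The consequence is stated in one direction only: "Should the estimated hazard rate significantly exceed the null rate, we will consider halting the trial for concern about safety". Section 7.2 repeats it: "we will consider halting the trial for safety if the estimated hazard rate significantly exceeds the null rate". Neither section attaches an action or a claim to a hazard below the null, and no consequence is stated for the final look.

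The sample size justification in Section 6 uses the same 5% null against 17.5% for local-control failure, with 30 patients per stratum, "using a one-tailed exact binomial test with type I error rate 10" percent.

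The plan does not say whether the hazard test is exact, likelihood-ratio, score or Wald, or how the 2.5% is divided between the tails.

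**The concern.** A safety rule that can act only on an excess gains nothing from error rate placed on the low side. If the tails are equal, 1.25% per look is left to detect harm. The number of recurrences needed before the rule fires may then be higher than the stated 2.5% requires.

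This matters because it is the only test in the plan of the overall local-recurrence rate against 5%, and local control is a primary endpoint. The rest of the data analysis plan offers estimation and between-stratum logrank tests. A missed excess here could let omission of the primary-bed field look acceptable when it is not.

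**Working it through.** **Inputs.** From Section 6: 60 patients, 12 months of accrual, up to 24 months each; interim at median follow-up 1.5 years (range 1 to 2); null 5% and alternative 17.5% at two years; 2.5% two-tailed at each look. Assumed here: uniform entry, no dropout, constant hazard, follow-up counted from enrollment.

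**The plan's own figures.** Null hazard: −ln(0.95)/24 = 0.002137 per month, which rounds to the stated 0.00214. For the separate binomial calculation with 30 patients, rejecting at 4 or more failures gives exact type I error 6.1% and power 79.5%, close to the stated 78%.

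**Error rate on the harm side, equal tails.** Per look 2.5%/2 = 1.25%. Over two looks, treated as independent: 1 − 0.9875² = 2.48%. If each 2.5% were one-sided: 1 − 0.975² = 4.94%.

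**The low side.** Expected null recurrences are 60 × 18 × 0.002137 = 2.31 at the interim and 60 × 24 × 0.002137 = 3.08 at the end. Zero recurrences then has probability e^−2.31 = 9.9% and e^−3.08 = 4.6%. Both exceed 1.25%, so an equal-tailed exact test cannot reject downward. This is specific to the exact test: a likelihood-ratio test with zero events gives √(2 × 3.08) = 2.48 at the end, above the 1.25% cut-off of 2.24. It would reject, but no action follows.

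**Triggers.** Each recurrence shortens person-time, by about 9 months at the interim and 12 at the end on average. μ is the expected null count after that reduction.

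- Interim, 6 events: μ = (1080 − 54) × 0.002137 = 2.19. Exact upper tail just under 2.5%; likelihood-ratio z = √{2[6 ln(6/2.19) − 3.81]} ≈ 2.11; score z = 3.81/√2.19 ≈ 2.57.
- Interim, 7 events: μ = (1080 − 63) × 0.002137 = 2.17. Exact upper tail about 0.7%.
- Final, 7 events: μ = (1440 − 84) × 0.002137 = 2.90. Exact upper tail about 2.9%; likelihood-ratio z = √{2[7 ln(7/2.90) − 4.10]} ≈ 2.03; score z = 4.10/√2.90 ≈ 2.41.
- Final, 8 events: μ = (1440 − 96) × 0.002137 = 2.87. Exact upper tail about 0.9%.

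The cut-offs are z = 2.24 (1.25%) and 1.96 (2.5%). At an upper 1.25%, exact and likelihood-ratio tests need about 7 then 8 events, while a score test already fires at 6 then 7. At an upper 2.5%, the likelihood-ratio test fires at 6 then 7. The exact test fires at 6 or 7 (depending on person-time) and then 8.

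**Detection.** Simulation, 100,000 trials per scenario; each cell shows upper 1.25% → upper 2.5%.

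| Statistic | Interim, true 17.5% | Either look, true 17.5% | Either look, true 10% |
|---|---|---|---|
| Exact Poisson | 70.9% → 78.5% | 85.8% → 87.6% | 26.8% → 31.2% |
| Likelihood-ratio | 71.0% → 83.1% | 85.8% → 92.8% | 26.9% → 42.3% |
| Wald | 41.2% → 56.3% | 62.8% → 75.7% | 7.8% → 15.1% |
| Score | 83.1% → 84.4% | 92.8% → 93.1% | 42.3% → 43.4% |
| Log-hazard Wald | 83.1% → 83.3% | 92.8% → 92.8% | 42.2% → 42.4% |

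**False alarms at a true 5%, either look.** About 1.2% as equal-tailed; about 2.1% for exact one-tailed; about 4% for likelihood-ratio one-tailed, whose actual per-look rate is about 2.6% to 3.0%, slightly above nominal.

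**The case against.** The strongest reply is that the plan may lose little or nothing, because it does not fix the test. Under a score or log-hazard Wald test, the two-tailed 2.5% rule already performs almost as well as its one-tailed version. Under a minimum-likelihood exact two-sided test, zero events is too probable to enter the rejection region, so the 2.5% already lies on the upper side and the loss is nil. This stands. A reader might infer that only 1.25% ever guards against harm, or that the rule as written needs 7 and then 8 recurrences. Both hold only for particular choices that the text leaves open.

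A reader might also infer that Section 6 contradicts itself, given the one-tailed 10% test in the sample size justification. The documents do not support that. It is a binomial calculation per stratum of 30, while the monitoring test is a pooled hazard test applied twice, and different tests may carry different error rates. The sample size paragraph supports treating the question as one-directional. It does not justify raising the per-look level to 5%, which would double the plan's stated level.

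A two-tailed test is also valid type I error control, the action is only to consider halting, and the Medical Monitor (Section 9.3) may recommend suspension independently. These points limit the severity. They do not give the low side a use.

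**Conclusion.** The point holds in a conditional form. The action is one-directional and the test is not. Putting the full 2.5% on the upper side cannot reduce the chance of flagging an excess, and for three of the five statistics examined it raises it materially. At a true 17.5%, the interim gain is about 12 points (likelihood-ratio), 8 (exact) or 15 (Wald), against about 1 or less for score and log-hazard Wald. At double the null rate (10%), either-look detection gains about 15 points with likelihood-ratio and about 4 with exact.

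These figures rest on equal tails, uniform accrual, a constant hazard and complete follow-up.

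A reader might infer that the present rule exposes more patients to harm. The documents do not support this: the interim falls one year after enrollment ends, and no action is stated for the final look. The stake is mainly the reliability of the trial's safety conclusion.

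**What to change.** In Section 6, Interim analysis, replace the two-tailed test by an upper one-tailed test at 2.5% at each look. Name the test statistic, and state the recurrence-count triggers that follow under full follow-up. With a likelihood-ratio test these are about 6 at the interim and 7 at the end. With an exact Poisson test they are 6 or 7 at the interim, depending on accumulated person-time, and 8 at the end. The exact test holds the 2.5% strictly; the likelihood-ratio test detects more but runs slightly over it, and the plan should say so if it is chosen. Keep the per-look level at 2.5%.

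The change is one or two sentences and needs no extra patients or data. Its price is a higher either-look false-alarm rate at a true 5%: from about 1.2% to about 2.1% (exact) or 4% (likelihood-ratio).

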5.4 Study Visit Schedule

Please see above in section 5.1. Patients will be followed on study for a period of approximately 2 years after completion of RT, after which time, routine follow-up will continue “off-study” per the discretion of the treating physicians. Patients will be followed for short and long term RT-associated toxicity and local and /or regional recurrence.

6 Statistical Plan

Study design

A total of 60 patients will be accrued over a total of 1.0 year. Patients will be followed on study for a period of approximately 2 years after completion of RT. After this time, patients will continue to be seen in follow-up by their treating physicians, per physician discretion according to physician and institutional practices.

Patients will be enrolled into two non-randomized treatment strata: IMRT (photon) and PBRT (proton). We anticipate enrolling approximately 30 subjects in each stratum given our recent experience with patterns of insurance approval for PBRT versus IMRT (please see rationale described above in the introduction regarding IMRT vs. PBRT. Patients will not be randomized to IMRT vs. PBRT, but rather the decision to treat with one modality versus another is based on insurance carrier approval status. .

Data analysis plan

The primary objectives of the study are to estimate the 2-year local (primary site) control rate at the primary tumor site, and 2-year rates of RT-associated toxicities (as measured by CTCAE, version 4.0 and patient-reported QOL). We will estimate the distributions of time of loss of local control and time to RT-associated toxicity by exact 95% confidence intervals. We will compare the distributions of time to local recurrence and time to toxicity between strata by the logrank test.

Secondary objectives include determining 2-year regional control, progression-free survival (PFS), metastasis-free survival (MFS), and overall survival (OS). Differences between intensity-modulated radiation therapy and proton therapy with respect to disease-related outcomes and toxicity/HRQoL will also serve as secondary objectives. We will summarize data on regional control, PFS, MFS and OS using Kaplan-Meier curves; estimate proportions of toxicities by 95% exact confidence intervals; and make comparisons between treatment strata by the logrank test.

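### The final test is dated two years after enrollment ends, before about 7 to 8 of the 60 patients can reach their 24-month post-RT visit

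*Combined protocol and SAP*

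**What the plan says.** Section 6, Interim analysis, describes "following each subject for up to 24 months" without saying from when. It places the interim look one year after enrollment ends, "when the median follow-up is 1.5 years (minimum = 1 and maximum = 2 years". The final test is then dated: "We will conduct the test when follow-up is complete (two years after completion of enrollment), again at the 2.5% type I error rate".

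The rest of the protocol counts from the end of radiation. Section 6 (Study design), like Section 5.4, says: "Patients will be followed on study for a period of approximately 2 years after completion of RT". Section 5.1 schedules clinical, toxicity and QOL evaluations at baseline, at completion of RT, and "then at approximately 3, 6, 12, 18 and 24 months after completion of RT"; the HRQoL paragraph of Section 6 repeats that schedule. Section 8.3 puts the off-study point at the same place: "At approximately 24 months after completion of RT, the subject will be considered" off study.

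Section 8.3 also puts treatment planning after enrollment, and Section 5.3 gives the length of RT: "Treatment will be continuous, 5 days per week for 6-7 consecutive weeks". No section gives the interval from enrollment to the start of RT, and none defines time zero for local control or toxicity.

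**The concern.** The protocol uses two follow-up clocks. Section 6 calls follow-up complete on a date counted from enrollment, while the visit schedule and the on-study period are counted from the end of RT. The most recently enrolled patients spend their first weeks in planning and treatment, so they cannot be 24 months past RT when the last-enrolled patient is 24 months past enrollment.

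Both primary endpoints (Section 3.2) are 2-year endpoints. The synopsis plans exact 95% intervals for the two-year control proportion and for toxicity proportions, and the sample size rests on an exact binomial test of 2-year local failure. Fixed-time binomial methods need each patient's status at the fixed time and make no allowance for censoring. If the data are cut on the stated date, the latest patients will typically have the 18-month visit as their last scheduled toxicity grade and QOL form.

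**Working it through.** **Inputs from the documents**
- Accrual (Section 6, Study design): "A total of 60 patients will be accrued over a total of 1.0 year". If uniform, 60/12 = 5 patients per month.
- RT duration (Section 5.3): 6-7 weeks. At 30.44 days per month, 42/30.44 = 1.38 months and 49/30.44 = 1.61 months.
- Final test: 24 months after the last enrollment. Last scheduled visit: about 24 months after RT.

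**Assumed:** 0 to 4 weeks from enrollment to the start of RT. The documents give the order of events but not the interval.

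**1. Which clock does the Interim analysis paragraph use?** One year after a uniform 12-month accrual ends, follow-up counted from enrollment is:
- minimum 12 months, median 12 + 6 = 18, maximum 24, that is 1 / 1.5 / 2 years.

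This reproduces the stated figures exactly. Counted from the end of RT, with no planning time, each figure falls by 1.38-1.61 months, to about 10.4-10.6 / 16.4-16.6 / 22.4-22.6 months, which does not match. The paragraph is counting from enrollment. (Its null hazard also reproduces: -ln(0.95)/24 = 0.00214 per month.)

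**2. Patients short of 24 months post-RT at the stated date** = 5 x L, where L is the time in months from enrollment to the end of RT.

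| Time from enrollment to end of RT | L (months) | Patients short | Share of 60 |
|---|---|---|---|
| RT only, 6 weeks | 1.38 | 6.9 | 11.5% |
| RT only, 7 weeks | 1.61 | 8.0 | 13.4% |
| RT 6 weeks + 4 weeks planning | 2.30 | 11.5 | 19% |
| RT 7 weeks + 4 weeks planning | 2.53 | 12.6 | 21% |

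The last-enrolled patient has 24 - L = 22.6 down to 21.5 months of post-RT observation on that date. The last 24-month visit falls 24 + L = 25.4 to 26.5 months after enrollment ends.

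**3. Effect on the exponential test.** If follow-up is counted from the end of RT to 24 months, person-time lost is 5 x L²/2: 5 x 1.38²/2 = 4.8 person-months, up to 5 x 2.53²/2 = 16.0. Against 60 x 24 = 1440 person-months that is 0.3% to 1.1%.

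**4. Illustration for the 2-year proportion,** if every patient short of the visit is dropped. With 3 local failures, the upper Clopper-Pearson 95% limit is:
- 13.9% for 3/60;
- 15.7% for 3/53 and 15.9% for 3/52 (RT duration only);
- 16.5% for 3/50 (10 patients short, which needs some planning time).

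Part of that movement is the point estimate, which goes from 3/60 = 5% to 3/50 = 6% because the failures stay and the denominator shrinks.

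**5. Illustration for HRQoL,** using the two-sample t test of the sample-size section (two-sided 5%, 90% power). With 30 per stratum the detectable effect computes as 0.85, against 0.86 in the plan. With 26 per stratum it is 0.92, and with 25 it is 0.94.

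**The case against.** The strongest reply is that the date is attached to one test only. The sentence concerns the exponential hazard test, which accepts censored times, and on the enrollment clock that the paragraph uses every patient has 24 months of potential follow-up. The two-year date is in parentheses after a condition, that follow-up be complete, so it could be read as an approximate date for an analysis that waits. Sections 5.1, 5.4 and 8.3 still commit to collecting the last visits. All of this stands for the hazard test. It does not remove the conflict, because the parenthesis defines completeness by a date on which the scheduled follow-up cannot be complete, and the plan names no other final date for the proportions or HRQoL.

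A reader might infer that 8 to 12 patients will certainly lack the visit. The documents alone support about 7-8. Reaching 12 needs roughly 3.4-4.4 weeks of planning, which no section states, and approximate visit timing could pull the count down.

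A reader might also infer that the affected patients contribute nothing, so that the analysis rests on 50 patients, or 25 per stratum. The documents do not support that either. These patients have more than 21 months of post-RT observation, and any earlier recurrence or toxicity is already known. The synopsis plans Kaplan-Meier curves for time to local recurrence and time to toxicity, and Section 6 plans mixed linear models for HRQoL over all visits; both use partial follow-up. The 16.5% limit and the 0.94 effect are worst-case illustrations of complete-case analysis at a common cutoff.

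Finally, moving every clock to completion of RT would create a gap of its own. Section 4.6 allows patients to refuse further treatment, and those who never finish RT would then have no time zero, while recurrences before the end of RT would fall outside the clock. That objection stands and shapes the fix.

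**Conclusion.** The conflict is certain: the stated final date precedes the last 24-month post-RT visits. Its size is modest. About 7-8 of 60 patients (12-13%) are affected on the documents' own figures, rising to about 12-13 if planning takes up to 4 weeks. These counts assume uniform accrual over 12 months, no earlier recurrence, death or dropout, and visits held close to schedule.

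The exponential test is barely affected. The consequence falls on the exact intervals for 2-year local control and toxicity and on the 24-month HRQoL data, and only if they share this cutoff. The plan neither says that they do nor gives them another date. The change is worth making because it is cheap and secures the 24-month assessment for patients who would otherwise stop at their 18-month visit in the final dataset. It does not call the design or the hazard test into question.

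**What to change.** 1. Redefine the trigger in Section 6: the final analysis takes place when the last patient has completed the 24-month post-RT visit or left the study. State that the 2-year proportions, toxicity and HRQoL analyses use the same data cutoff.
2. State one time origin for each 2-year time-to-event endpoint, chosen so that patients who do not complete RT and recurrences before the end of RT are still counted. Enrollment is one such origin. The visit schedule can stay anchored to the end of RT.
3. Make the interim minimum, median and maximum follow-up consistent with that origin. If it is enrollment, the present 1 / 1.5 / 2 years can stay and only the origin needs naming.

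The cost is a final analysis about 1.4-2.5 months later than now stated and a few sentences of wording. No extra patients or visits are needed.
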